7. NOTATION OF TREATMENT GROUPS AND VISITS

The following notation of treatment groups will be used throughout the report:

TABLE 1 NOTATION OF TREATMENT GROUPS

Full notation (as used in the study protocol)	Notation used throughout all tables, listings, and figures
100 mg/day of CT1812	CT1812 100 mg
300 mg/day of CT1812	CT1812 300 mg
100mg/day and 300mg/day of CT1812 combined	CT1812 Combined
Placebo	Placebo

TABLE 1 VISIT TERMINOLOGY

Visit	Notation used throughout all tables, listings, and figures
Screening, Days -42 through Day -1, Visit V1	Screening
Baseline, Day 1, Visit V2	Baseline
Day 14 (±2), Visit V3	Day 14
Day 28 (±2), Visit V4	Day 28
Day 42 (±2), Visit V5	Day 42
Day 56 (±2), Visit V6	Day 56
Day 70 (±2), Visit V7	Day 70
Day 98 (±2), Visit V8	Day 98
Day 126 (±2), Visit V9	Day 126
Day 154 (±2), Visit V10	Day 154
Early Termination, Day 182 (±2), Visit V11	Day 182
Safety Follow-up, Day 210 (+2), Visit V12	Follow-up

Analysis Days

Study days are measured from the date of first dose of randomized treatment.

Study days corresponding to measurements are calculated as:

- Assessment date – date of first exposure to treatment + 1 (if assessment date is on or after the date of first exposure to treatment)
- Assessment date – date of first exposure to treatment (if assessment date is before the date of first exposure to treatment)

## 8. ANALYSIS POPULATIONS

The populations for analysis will include the enrolled population, intent-to-treat (ITT) population, safety population, completers/compliers population, pharmacokinetic (PK) population, pharmacodynamics (PD) population, and the skin biopsy population.

- The enrolled population will include all subjects that signed the Informed Consent Form (ICF). Subject disposition summaries and data listings will be based on this population.
- The safety population will include all subjects in the ITT population who received at least one dose of study drug. Subjects in this population will be analyzed according to the treatment they received, regardless of which treatment they were randomly assigned. All safety and tolerability analyses will be based on this population and treatment assignment.
- The ITT population will include all subjects that were randomly assigned to study drug. Subjects in this population will be analyzed according to the treatment to which they were randomized, regardless of what treatment they received. All efficacy analyses will be based on this population and treatment assignment.
- The completers /compliers population will include all randomized subjects who completed the study (i.e., who did not prematurely withdraw) and had between 80%-120% compliance with study drug over the course of the study. There is no expectation that a subject included in the completers/compliers population will have attended every single scheduled visit; as long as the subject completed the study and met the study drug compliance criteria, they will be included in the population. Subjects in this population will be analyzed according to the treatment to which they were randomized, regardless of what treatment they received. This population will be used for sensitivity analyses of the efficacy endpoints.

The following subject populations will be used for PK/PD analyses:

- The PK population will include all subjects in the safety population who had at least 1 quantifiable concentration of CT1812.
- The PD population will include all subjects in the safety population who had an exploratory biomarker evaluation.

The following subject population will be used for the summarization of skin biopsy results:

- The skin biopsy population will include all subjects in the safety population with Syn-One Test skin biopsy results available.

## 9. STUDY DEMOGRAPHICS, BASELINE CHARACTERISTICS, AND STUDY CONDUCT

### 9.1 Subject Disposition

Subject disposition information will be summarized by treatment group and overall. Summaries will include the number of subjects screened, enrolled, randomized, included in each analysis population, completing the study treatment, discontinuing study treatment and the reason for discontinuing study treatment, completing the study, discontinuing the study and the primary reason for study discontinuation.

### 9.2 Protocol Deviations

Major protocol deviations that could potentially affect the efficacy or safety conclusions of the study will be identified before database lock and unblinding of individual subject treatment information. Major protocol deviations may include, but are not limited to:

- Randomized subjects who did not satisfy selected inclusion and exclusion criteria
- Randomized subjects who developed withdrawal criteria during the study but were not withdrawn
- Subjects who received the wrong treatment or an incorrect dose
- Subjects who missed visit or visit outside protocol window
- Subjects who missed assessment or assessment at incorrect time point
- Subjects who were administered prohibited medication

Major protocol deviations will be summarized by deviation category, deviation subcategory and treatment group for the ITT population.

### 9.3 Eligibility

A listing of subjects not fulfilling eligibility criteria will be presented.

### 9.4 Demographic and Baseline Characteristics

Demographic variables include age, sex, ethnicity, and race. Age will be calculated in years relative to the informed consent date.

Other baseline characteristics include height, weight, time since DLB diagnosis, BMI, Geriatric Depression Scale (GDS), MMSE scores, Modified Hoehn and Yahr Scale, Apolipoprotein Genotype, Amyloid Probability Score 2, and MDS-UPDRS3 Total Score.

Descriptive statistics will be presented for age, height, weight, and other continuous variables. Frequency counts and percentages will be presented for sex, ethnicity, and race. Demographic

and baseline characteristics will be listed for each subject and summarized descriptively by treatment group for the safety and ITT populations.

The time since DLB diagnosis is calculated by (date of first exposure to treatment - date of probable DLB Diagnosis + 1)/365.25.

An additional table will be produced to summarize baseline scores for efficacy assessments for the ITT population.

## 9.5 Medical History

The verbatim terms of the reported medical history conditions/events will be coded using the Medical Dictionary for Regulatory Activities (MedDRA), version 24.1.

A summary table will be prepared by treatment group and overall for the ITT Population. The summary will show the system organ class (SOC) and preferred term (PT) ordered by descending frequency in the overall column by SOC and PT.

## 9.6 Prior and Concomitant Medications

Prior and concomitant medication verbatim terms will be mapped to the World Health Organization (WHO) Anatomical Therapeutic Chemical (ATC) classification 3 and preferred names using the WHO Drug Global dictionary (enhanced) September 2021.

Partial dates will be imputed. For details on imputation rules, refer to Appendix A: Presentation of Data and Programming Specifications. Imputed dates are only used for classification of a medication as a prior or concomitant medication; no other calculation, such as durations, will be performed using imputed dates.

- Medications that started prior to the first dose of study drug will be considered prior medications, regardless of whether or not they were stopped prior to the first dose of study drug.
- Any medications continuing or starting after the first dose of study drug will be considered concomitant medications.
- If a medication starts prior to the first dose of study drug and continues after the first dose of study drug, it will be considered both prior and concomitant.

If the medication cannot be classified as a prior or concomitant medication, the medication will be considered as concomitant.

Prior and concomitant medications will be summarized for each treatment by ATC class 3 and preferred name for the ITT population. These summaries will present the number and percentage of subjects using each medication. Subjects may have more than 1 medication per ATC class and preferred name. At each level of subject summarization, a subject is counted once if he/she reported 1 or more medications at that level. Each summary will be ordered by descending subject count in the total column by ATC level 3 and preferred name.

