3.2.2 Nonclinical Pharmacokinetic Studies

Absorption of CT1812 following oral gavage administration to mice, rats and dogs appears to be very rapid, with brain concentrations exceeding those concurrently measured in plasma. The drug is highly protein-bound in plasma from rat, mouse, dog, and human, but only weakly bound to blood cells. Systemic exposures to CT1812 following oral administration to rats and dogs were greater than dose-proportional at high, toxicologically relevant dosages. Extensive first-pass metabolism appears to be via oxidation and/or direct glucuronidation.

Studies with human recombinant cytochrome P450 (CYP) isoforms show rapid metabolism ($t_{1/2}$ of 6.8 min) by CYP3A4, and slower metabolism ($t_{1/2}$ of 57 and 81 minutes) by CYP2D6 and CYP2C19. A direct glucuronide conjugate was also observed *in vitro* in human hepatocyte incubations, consistent with that observed *in vivo* in rats and dogs.

CT1812 was not an inhibitor of CYP1A2, CYP2B6, or CYP2C8, with less than 50% inhibition of activity observed at the highest concentration evaluated (10 μ M). CT1812 was a weak inhibitor of CYP2C9, CYP2C19, CYP2D6, and CYP3A4, with IC₅₀ values ranging from 4.4 to 38 μ M. However, when evaluated in the context of systemic exposure data in humans, the drug-drug interaction liability from these effects was considered to be minimal. CT1812 was found to be an inducer of CYP3A4 (\geq 0.3 μ M), suggesting a potentially clinically significant risk of drug-drug interactions with this isoform, but induction of CYP2B6 and CYP1A2 appear less likely. CT1812 does appear to be a substrate for p-glycoprotein (P-gp), and inhibits P-gp with an IC₅₀ of 10 μ M. This is considered to be potentially clinically significant, primarily due to the possibility of interactions in the gastrointestinal (GI) tract. *In vitro* inhibition of the OATP1B1 transporter (IC₅₀

of 11.5 μM) by CT1812 does not appear to be clinically relevant, when evaluated in the context of systemic exposure data in humans. As assessed per the FDA 2012 draft guidance for drug-drug interaction (DDI) evaluations, clinically relevant DDI are suggested via CT1812 effects on CYP3A4 and P-gp.

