5.2 Endpoints

5.2.1 Safety Endpoints

- The incidence and severity of adverse events.
- The change in usage of concomitant medications.
- Changes in vital signs.
- Changes in physical exam findings.
- Changes in electrocardiogram findings.
- Changes in clinical laboratory testing (serum chemistry, hematology, urinalysis).
- Changes in the Columbia Suicide Severity Rating Scale (C-SSRS).

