9.3 Concomitant Medications and Other Restrictions

All medications mentioned in the exclusion criteria (Section 8.3) are expressly prohibited at any time during the study. Exceptions to the list of excluded medications may be made on a case-by-case basis if discussed and approved by the medical monitor in advance. Intake of drugs or substances potentially involved in clinically significant CYP3A4 or P-gp mediated drug interactions with CT1812, within 4 weeks or five half-lives of the interacting drug prior to administration of CT1812 and throughout the course of the study are prohibited. Grapefruit juice should be avoided in the two weeks prior to dosing and throughout the course of the study. See Appendix A for a list of these prohibited substances. As noted in Appendix A, The P-glycoprotein (P-gp) substrate drugs loperamide and talinolol must be separated from dosing of CT1812 (before or after) by 6 hours. If this is not feasible, the subject cannot participate in the study.

Subjects may be on stable doses (at least 30 days prior to screening) of an acetylcholinesterase inhibitor and/or memantine and continue these medications during the study. Subjects may be enrolled on stable doses (at least 30 days prior to screening) of atypical antipsychotics (e.g., quetiapine, pimavanserin) and clonazepam; however, such subjects should be monitored for potential changes in symptoms related to the use of these medications as a result of possible drug-drug interactions. Dose adjustments to these medications may be considered if indicated.

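### Change in concomitant medication use is a protocol safety endpoint, but no planned table summarizes change: SAP 9.6 counts any use only

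*SAP*

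**What the plan says.** Protocol 5.2.1 lists seven safety endpoints, one of which is "The change in usage of concomitant medications". The visit procedures in Protocol 9.2 have sites record medication changes at every visit after baseline. Protocol 9.3 gives a reason to look at change. Of subjects on atypical antipsychotics or clonazepam it says "such subjects should be monitored for potential changes in symptoms related to the use of these medications as a result of possible drug-drug interactions", and it allows the doses of those drugs to be adjusted. The pharmacological background is in Protocol 3.2.2: "CT1812 was found to be an inducer of CYP3A4".

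The analysis side says less. Protocol 14.4.2 promises only that concomitant medications will be coded and summarized. SAP 9.6 sets the classification: "Any medications continuing or starting after the first dose of study drug will be considered concomitant medications". If a drug begun earlier "continues after the first dose of study drug, it will be considered both prior and concomitant". On the output, "These summaries will present the number and percentage of subjects using each medication", and at each level "a subject is counted once if he/she reported 1 or more medications at that level". The tables are "summarized for each treatment by ATC class 3 and preferred name for the ITT population". SAP 15, which holds the safety analyses, has no medication section. SAP 16, which lists departures from the protocol, mentions only added analysis populations.

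**The concern.** The endpoint is a change, and the planned statistic is any use. A stable long-term drug, a drug stopped on study, a drug whose dose was altered and a drug newly begun each add the same single count. Safety and tolerability is the primary objective, so one of its listed endpoints would reach the study report without a between-arm summary of the quantity named. The data for at least part of that summary are collected visit by visit.

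There is also a population mismatch. SAP 8 and SAP 15 assign safety analyses to the safety population, as treated, while SAP 9.6 uses the ITT population, as randomized.

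**Working it through.** The plan gives no figure for medication use, so there is none to reproduce. The first three steps compare the passages, and the fourth is an illustration on assumed rates.

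**1. Endpoints against analyses.** Six of the seven endpoints in Protocol 5.2.1 have a home in SAP 15: adverse events (15.1), laboratory tests (15.3), vital signs (15.4), physical examination (15.5), ECG (15.6) and C-SSRS (15.7). Change in concomitant medication use has none. SAP 10.6 uses AChE inhibitor or memantine intake as a subgroup factor, but that too is a yes/no for any use.

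**2. What the SAP 9.6 concomitant table registers for one subject.**

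| Course after first dose | Count |
|---|---|
| Existing drug, unchanged | 1 |
| Existing drug, dose changed | 1 |
| Existing drug, stopped on study | 1 |
| New drug, class not used before | 1 |
| Second drug in a class already used | no addition at class level |

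For an existing user, a dose change or a stop shifts the table by 1 − 1 = 0, at any rate.

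**3. Can new starts be recovered?** In the dataset, yes: a drug that is concomitant but not prior is a new start. From the two planned tables, only approximately. For a given drug or class, let C be subjects counted as concomitant, P those counted as prior, S those with use after first dose but none before, and D those whose use ended before first dose. Then C − P = S − D.

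Example with assumed counts: 8 of 40 subjects per arm use a class at baseline, and 4 more start it on 300 mg.
- With D = 0, the prior tables show 8 and 8, and the concomitant tables show 12/40 = 30% and 8/40 = 20%. The difference 12 − 8 = 4 reveals the new starts.
- If 4 other subjects on 300 mg had stopped the class before first dose, P = 12 and C − P = 0, and the 4 starts disappear.
- If instead 4 of the 8 existing users had a dose change, both arms show 8/40.

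**4. Dilution where baseline use exists (assumed rates).** Let b be the share already using the class at first dose and p the new-start rate among non-users. The table shows b + (1 − b)p. For b = 10%, p = 5% and 20%: 0.10 + 0.90 × 0.05 = 14.5% and 0.10 + 0.90 × 0.20 = 28.0%, a ratio of 28.0/14.5 = 1.93.

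| b | Shown, p = 5% vs 20% (true ratio 4.00) | Ratio | Ratio shown, p = 10% vs 25% (true ratio 2.50) |
|---|---|---|---|
| 0 | 5.0% vs 20.0% | 4.00 | 2.50 |
| 10% | 14.5% vs 28.0% | 1.93 | 1.71 |
| 30% | 33.5% vs 44.0% | 1.31 | 1.28 |
| 50% | 52.5% vs 60.0% | 1.14 | 1.14 |
| 70% | 71.5% vs 76.0% | 1.06 | 1.06 |

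The plan tests none of this, but power gives a gauge. Compare 40 placebo with 80 CT1812 subjects, two-sided 0.05, normal approximation with pooled variance under the null, p = 5% vs 20%. Any use has power 0.37, 0.19 and 0.12 at b = 10%, 30% and 50%. New starts among non-users have 0.55, 0.43 and 0.30. At b = 0 both have 0.60.

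**The case against.** The case against is substantial, and most of it stands as a limit on the claim.

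- **Reporting.** A reader might infer that the endpoint is never reported. The documents do not support that. Medications are tabulated by arm, the protocol synopsis also promises a listing, and SAP 6 lists all eCRF data by subject. Protocol 14.4.2 itself asks only for a summary, so the gap begins in the protocol.
- **New starts.** They are derivable, and the prior and concomitant tables read together would largely show them. The stability requirements before entry should keep D small.
- **Hidden signal.** A reader might also infer that a drug-interaction or symptom signal would be concealed. That goes too far. The NPI hallucination and delusion domains are summarized and tested (SAP 11.8), and adverse events are tabulated by term and severity (SAP 15.1). A new antipsychotic falls under exclusion 17 unless the medical monitor approves an exception, and SAP 9.2 names prohibited medication as a possible major deviation, summarized by arm.
- **Interaction risk.** The human study in Protocol 3.3 used 560 mg, above both trial doses. It found a 24% fall in midazolam AUC, called the interaction weak and judged clinical implications unlikely.
- **Population.** ITT and safety tables differ only for subjects who were randomized but not dosed, or who received the wrong treatment.

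What these points leave untouched: listings for about 120 subjects are not a between-arm summary. Approved exceptions may never appear as deviations, and the dose adjustments that Protocol 9.3 allows are not plainly deviations. NPI and adverse event tables measure symptoms, not medication change. The monitoring instruction in Protocol 9.3 stands despite the weak interaction.

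**Conclusion.** The point holds in a limited form. A listed safety endpoint has no analysis that summarizes it, and SAP 16 does not say so. Two consequences need no assumption: on-study stops, and dose changes in existing users, cannot show in the SAP 9.6 table. A third depends on rates the documents do not give: new starts are diluted in proportion to baseline use, from not at all when nobody uses the class to nearly completely when most do. The illustrated ratios run from 4.00 down to 1.06 and are not estimates for this trial.

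Two things cannot be checked from the text. The eCRF is not included, so whether dose is captured is an assumption. The body of the table index in SAP Appendix C is not shown, so a table title there cannot be excluded, although no method in the body of the SAP would support one.

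No test or decision in the plan rests on this endpoint. It is a gap in safety reporting, not a threat to the efficacy result.

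**What to change.** Add to SAP 15 one table in the safety population, by arm, giving n (%) of subjects with a medication newly started, stopped, or (where the eCRF captures it) changed in dose after the first dose. Show it by ATC level 3, with separate rows for antipsychotics, clonazepam, and AChE inhibitors/memantine. Define a new start as a drug that is concomitant but not prior. Keep the SAP 9.6 tables as background description. If the sponsor prefers not to add the table, SAP 16 should state that this endpoint will be listed only.

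The cost is one extra descriptive table from records that the visits already generate. No procedure and no treatment rule changes. Given the power figures above, the table should be read descriptively. It should be specified before unblinding, because SAP 6 labels later analyses post hoc.

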## 10. EFFICACY ANALYSES

All efficacy analyses will be based on the ITT population. As a sensitivity analysis, all efficacy endpoints will be summarized using the completers/compliers population.

### 10.1 Efficacy Endpoints

Efficacy endpoints are listed below:

- MoCA
- Epworth Sleepiness Scale (ESS)
- Clinician Assessment of Fluctuation (CAF)
- ADCS-Clinical Global Impression of Change (CGIC)
- ADCS-Activities of Daily Living (ADCS-ADL)
- Movement Disorder Society – United Parkinson's Disease Rating Scale Part III (MDS-UPDRS Part III)
- Cognitive Drug Research Battery (CDR)
- Neuropsychiatric Inventory (NPI)

#### 10.1.1 Montreal Cognitive Assessment Scale (MoCA)

The MOCA is a brief dementia screening assessment that covers nine domains (Nasredinne et al., 2005). The MOCA has a 0-30 range with lower scores meaning more impairment. Total score is calculated by summing all sub-scores listed on the right-hand side. Add one point for an individual who has 12 years or fewer of formal education, for a possible maximum of 30 points. A final total score of 26 and above is considered normal. Total score is obtained directly from CRF.

#### 10.1.2 Epworth Sleepiness Scale (ESS)

The Epworth Sleepiness Scale (ESS) is a measure that assesses subjective sleepiness over the prior two weeks (Johns, 1991,1997). The ESS is a scale that queries the likelihood of dozing (i.e., 0= no chance of dozing, 1= slight chance of dozing, 2= moderate chance of dozing or sleeping, 3= high chance of dozing) in eight different circumstances. Total score sums up all sub-scores and can range from 0 to 24. A higher score is associated with increased sleepiness. An ESS score  $\geq 10$  is considered abnormal and consistent with excessive daytime sleepiness. Total score is obtained directly from CRF.

### 10.1.3 Clinician Assessment of Fluctuation (CAF)

Cognitive fluctuations are a core feature of DLB (McKeith et al., 2017) characterized by alterations in attention, alertness, and consciousness. The CAF is a screening questionnaire asked of an informant to capture frequency and duration of episodes to calculate a severity score (range 0-16 with higher scores representing more severe fluctuations (Walker et al., Sep 2000). If the fluctuating confusion is present, the frequency and duration of episodes of fluctuating confusion are both rated on a scale of 0-4, and these two scores are multiplied together to produce a severity score from 0-12 (0 representing no fluctuating confusion, 12 representing severe fluctuating confusion; a score of 16 would signify a continuous clouded state, which, by definition, would denote no fluctuation).

